3.8. Visit Windows

3.8.1. Definition of Study Day

Study Day 1 is defined as the day of first dose of study drug which is also the Randomization visit.

Study day is the day relative to the first dose of study drug, calculated as:

Visit Date – Dose Date + 1, if Visit Date is on or after the First Dose Date

Visit Date – Dose Date, if Visit Date is prior to the First Dose Date

3.8.2. Analysis Windows

Subject visits might not occur on protocol-specified days. Therefore, for the purpose of analysis, observations will be assigned to visits based on the windows presented in Table 3-1. Day 1 is the day of first dose of study drug.

Table 3-1. Visit Windows for Peak VO₂, MLHFQ, Treadmill Exercise Time, Biomarker Data, CPET 12-Lead ECG, and ICD Interrogation

Visit	Target Day	Visit Window in Day(s)
Baseline		≤ 1
Week 12	84	2–126
Week 24	168	> 126

Table 3-2. Visit Windows for ECHO

Visit	Target Day	Visit Window in Day(s)
Baseline		≤ 1
Week 2	14	2-49
Week 12	84	50–126
Week 24	168	> 126

Table 3-3. Visit Windows for Arrhythmia Burden

Visit	Target Day	Visit Window in Day(s)
Baseline		< 1
Days 1–14	1	1–21
Weeks 6–8	42	22–84
Weeks 18–20	126	> 84

The target and window are based on the start date of the 14-day ZIO[®] XT Patch period.

Table 3-4. Visit Windows for 12-Lead ECG, Vital Signs, and Clinical Laboratory Data

Visit	Target Day	Visit Window in Day(s)
Baseline		≤ 1
Week 2	14	2–28
Week 6	42	29–63
Week 12	84	64–105
Week 18	126	106–147
Week 24	168	148–210
Week 36	252	211–294
Week 48	336	295–378
Week 60	420	379–462
Week 72	504	463–546
Week 84	588	> 546 – last dose date + 30 days

All visits, including Unscheduled, Early Termination, and Follow-up visits, will be eligible for inclusion in table summaries based on the windows presented in Table 3-1, Table 3-2, and Table 3-3.

In the efficacy summary tables, Peak VO₂, treadmill exercise time, MLHFQ, ECHO, QTc interval at rest and at Peak from the exercise ECG, and biomarker results will be summarized based on values obtained at the visit using the windows in Table 3-1 or Table 3-2.

For the safety summaries, all visits other than the Follow-up visit, including Unscheduled and Early Termination visits, will be eligible for inclusion in table summaries based on the windows presented in Table 3-4.

In the safety summary tables for 12-lead ECG and vital signs, data obtained after the last dose date plus 30 days will be excluded from the summaries, but will be included in the listings.

3.8.3. Selection of Data in the Event of Multiple Records in a Window

Depending on the statistical analysis method, single values may be required for each analysis window. A single value will be chosen based on the rules below.

If multiple nonmissing numeric observations exist in a window, a record will be chosen based on the following rules:

- For baseline, the last available record on or prior to the date of the first dose of study drug will be selected. If there are multiple records with the same time or no time recorded on the same day, average (arithmetic or geometric mean, as appropriate) will be used for the baseline value.
- For post baseline assessments:
 - The record closest to the target day for that visit will be selected.
 - If there are 2 records equidistant from the target, the later record will be selected.
 - If there is more than 1 record on the selected day, the average will be taken, unless otherwise specified.

4. SUBJECT DISPOSITION

4.1. Subject Enrollment

Subjects randomized will be summarized by number and percentage in each country and by each investigator within a country and by treatment group. The denominator for percentage calculation will be the number of randomized subjects. Similarly, the number and percentage of subjects enrolled in each randomization strata will be presented. If there is a discrepancy between the interactive voice/web response system (IXRS) and the electronic case report form (eCRF) regarding age or sex, the value calculated from the eCRF will be used and discrepancies between the IXRS and eCRF will be listed.

The number and percentage of subjects included in each analysis set (randomized, safety, FAS, PK analysis set and biomarker analysis set) will be presented. If applicable, the reasons for exclusion from the analysis sets will be summarized. The denominator for this calculation will be the number of randomized subjects.

4.2. Disposition of Subjects

A summary of subject disposition will be provided by treatment group. This summary will present the number of subjects screened, randomized, included in the safety analysis set, and the number and percentage of subjects meeting the following criteria:

- Completed Week 24
- Completed study drug through the double-blind period
- Did not complete study drug through the double-blind period, (with summary of reasons for discontinuation)
- Completed the double-blind study period
- Did not complete the double-blind study period (with summary of reasons for not completing the study period)

The denominator for the percentages of subjects in each category will be the number of subjects in the safety analysis set. In addition, a flowchart will be provided to depict the disposition.

Summaries will be provided by treatment group for the safety analysis set. No inferential statistics will be generated. A data listing of reasons for premature study treatment and study discontinuation will be provided.

4.3. Extent of Exposure

4.3.1. Duration of Exposure to Study Drug

Duration of exposure to study drug will be defined as (last dose date – first dose date + 1), regardless of temporary interruptions in study drug administration, and will be expressed in days. Duration of exposure to study drug will be summarized using descriptive statistics (sample size, mean, standard deviation, median, Q1, Q3, minimum and maximum) and as the number and percentage of subjects exposed for specific periods (eg, ≥ 1 day, ≥ 4 weeks, ≥ 8 weeks, ≥ 12 weeks, ≥ 16 weeks, ≥ 20 weeks, ≥ 24 weeks, ≥ 28 weeks, ≥ 32 weeks, ≥ 36 weeks, ≥ 40 weeks, ≥ 44 weeks, ≥ 48 weeks, ≥ 52 weeks, ≥ 56 weeks, ≥ 60 weeks, ≥ 64 weeks, ≥ 68 weeks, ≥ 72 weeks, ≥ 76 weeks, ≥ 80 weeks, and ≥ 84 weeks). First and last dose dates are determined from the Study Drug Administration eCRF page. In addition, the number and percentage of subjects with study drug reduced from 6 mg daily to 3 mg, temporarily interrupted, and drug permanently discontinued due to AE (based on the Study Drug Administration and Adverse Event eCRF pages) will be summarized.

Summaries will be provided by treatment group for the safety analysis set. No inferential statistics will be provided.

A by-subject listing of study drug administration will be provided separately by subject ID number (in ascending order) and visit (in chronological order).

4.4. Protocol Deviations

Subjects who did not meet the eligibility criteria for study entry, but were enrolled in the study will be summarized regardless of whether they were exempted by the sponsor or not. The summary will present the number and percentage of subjects who did not meet at least 1 eligibility criterion and the number of subjects who did not meet specific criteria by treatment group based on the Safety Analysis Set. A listing will be provided for subjects in the randomized analysis set who violated at least one inclusion or exclusion criteria. The listing will include the criteria not met and related comments.

Protocol deviations occurring after subjects entered the study are documented during routine monitoring. The number and percentage of subjects with important protocol deviations by deviation reason (eg, nonadherence to study drug, violation of select inclusion/exclusion criteria) will be summarized by treatment group for the safety analysis set. A by-subject listing will be provided for those subjects with important protocol deviations.

5. BASELINE DATA

5.1. Demographics and Baseline Characteristics

Subject demographic data (age, sex, race, and ethnicity) and baseline characteristics (body weight, height, BMI, LVOT gradient, maximal LV wall thickness, baseline LV ejection fraction, presence of known sarcomeric mutation, Peak VO₂, QTcB, CCS class, NYHA class of dyspnea, use of beta-blockers, and use of calcium channel blockers) will be summarized by treatment group and overall using descriptive statistics (sample size, mean, standard deviation, median, Q1, Q3, minimum and maximum) for continuous data and by the number and percent of subjects for categorical data. CCS Class is captured on the exertional symptoms eCRF page, presence of sarcomeric mutation is captured on the cardiovascular medical history eCRF page, use of beta-blockers and calcium channel blockers is captured on the prior and concomitant medications eCRF page, and adjudicated ECHO data (maximal LV wall thickness and baseline LV ejection fraction) will be provided by the core imaging laboratory. The summaries of demographic data and baseline characteristics will be provided for the safety analysis set. No inferential statistics will be provided.

5.2. Medical History

Cardiovascular history and risk factors (diabetes mellitus, dyslipidemia, smoking status) will be collected on the eCRF and will be summarized by treatment group and overall by the number and percentage of subjects with each condition. Summaries of cardiovascular history and risk factors will be provided for the safety analysis set. No inferential statistics will be generated.

Other medical history (ie, conditions not specific to the disease being studied) data will be listed only. General medical history data will not be coded.

6. EFFICACY ANALYSES

6.1. Definition of the Primary Efficacy Endpoint

The primary efficacy endpoint is the change in Peak VO₂ from baseline to Week 24. Data will be sent to the core exercise physiology laboratory from the sites and the core exercise physiology laboratory will provide adjudicated results to Gilead. The adjudication process at the core exercise physiology laboratory will be blinded to treatment assignment.

6.2. Statistical Hypothesis for the Primary Efficacy Endpoint

H₀: $\mu_{\text{Eleclazine}} = \mu_{\text{Placebo}}$

(ie, the difference between the mean change from baseline in Peak VO₂ in eleclazine and placebo groups is zero)

H_a: $\mu_{\text{Eleclazine}} \neq \mu_{\text{Placebo}}$

(ie, the difference between the mean change from baseline in Peak VO₂ in eleclazine and placebo groups is not zero)

6.3. Analysis of the Primary Efficacy Endpoint

Peak VO₂ at baseline, Week 24, and change from baseline at Week 24 will be summarized by treatment group (eleclazine or placebo) for the FAS with the following descriptive statistics: sample size, mean, standard deviation, median, minimum, maximum, Q1 and Q3. The change in Peak VO₂ from baseline to Week 24 for the eleclazine treatment group will be compared to that of the placebo treatment group using analysis of covariance (ANCOVA) including terms for baseline Peak VO₂, sex, and age (continuous). This analysis will be performed on the FAS. Missing data will not be imputed.

The assumption of normality for the ANCOVA analyses will be assessed with the Shapiro-Wilk statistic and residuals will be visually examined for heterogeneity via scatter plots. If the normality assumption is violated, treatment differences will be assessed using an ANCOVA model on the rank-transformed change from baseline values.

6.4. Secondary Efficacy Endpoints

6.4.1. Definition of Secondary Efficacy Endpoints

Secondary efficacy endpoints include:

- Change in MLHFQ between baseline and Week 24.
 - If there are no missing items, the MLHFQ score is computed by adding the values for all 21 items. Each item is measured on a 6-point Likert scale (0 to 5) with higher values being worse. If more than half of the items are missing, the score is missing. If less than half of the items are missing, the score is computed as follows: $(\sum \text{nonmissing items} / \text{number of nonmissing items}) * 21$

- Change in treadmill exercise time between baseline and Week 24
- Change in Peak VO₂ between baseline and Week 12
- Change in MLHFQ between baseline and Week 12
- Change in treadmill exercise time between baseline and Week 12

6.4.2. Analysis Methods for Secondary Efficacy Endpoints

The secondary efficacy endpoints will be summarized and analyzed in a manner similar to the primary efficacy endpoint.

The FAS will be used for the analysis of all secondary efficacy endpoints.

6.5. Exploratory Efficacy Endpoints

6.5.1. Definition of Exploratory Efficacy Endpoints

PPD

[Redacted content]

•PPD

6.5.2. Analysis Methods for Exploratory Efficacy Endpoints

PPD

6.6. Changes From Protocol-Specified Efficacy Analyses

The primary and secondary endpoints will be tested at a 2-sided nominal significance level of 0.05, with no adjustment for multiple testing. No inferential statistics will be provided for exploratory endpoints. The sensitivity analyses of secondary efficacy endpoints using Mixed Models Repeated Measures (MMRM) will not be performed. Missing values will not be imputed. Correlations between efficacy endpoints will not be explored, and subgroup analyses will not be performed. The following ECHO efficacy endpoints specified in the protocol will not be summarized: mitral E velocity, mitral a velocity, mitral deceleration time, mitral regurgitation severity, LA volume index, Tei myocardial performance index, and maximal LV wall thickness.

6.7. Summary of Efficacy Analyses

The analyses of the efficacy endpoints are summarized in the following table:

Table 6-1. Summary of Efficacy Analyses

Endpoint Description	Analysis Set	Analysis Method
Primary: Δ Peak VO ₂ at Week 24	FAS	ANCOVA
1 st Secondary: Δ MLHFQ at Week 24	FAS	ANCOVA
2 nd Secondary: Δ treadmill exercise time at Week 24	FAS	ANCOVA
3 rd Secondary: Peak VO ₂ at Week 12	FAS	ANCOVA
4 th Secondary: Δ MLHFQ at Week 12	FAS	ANCOVA
5 th Secondary: Δ treadmill exercise time at Week 12	FAS	ANCOVA
Exploratory Endpoints		
PPD		
		
		
		

Δ is the change from baseline.
 The ANCOVA model will include terms for age, sex, baseline value, and treatment.

7. SAFETY ANALYSES

Formal statistical comparisons between treatment groups are not planned for safety analyses.

7.1. Adverse Events and Deaths

7.1.1. Adverse Event Dictionary

Clinical and laboratory adverse events (AEs) will be coded using the Medical Dictionary for Regulatory Activities (MedDRA). System organ class (SOC), high level group term (HLGT), high level term (HLT), preferred term (PT), and lower level term (LLT) will be attached to the clinical database.

7.1.2. Adverse Event Severity

AEs are graded by the investigator as mild, moderate, or severe according to guidelines specified in the study protocol. The severity grade of events for which the investigator did not record severity will be categorized as “missing” for tabular summaries and data listings, and will be considered the least severe for the purposes of sorting for data presentation.

7.1.3. Relationship of Adverse Events to Study Drug

Related AEs are those for which the investigator selected “Related” on the AE CRF to the question of “Related to Study Treatment.” Relatedness will always default to the investigator’s choice, not that of the medical monitor. Events for which the investigator did not record relationship to study drug will be considered related to study drug. Data listings will show relationship as missing.

Adverse events related to study procedures are those for which there are facts/arguments to suggest a reasonable possibility that there is a causal relationship of the AE to one or more study procedures.

7.1.4. Serious Adverse Events

Serious adverse events (SAEs) are those identified as serious in the clinical database. The clinical database will be reconciled with the SAE database from the Drug Safety and Public Health Department before database finalization.

7.1.5. Treatment-Emergent Adverse Events

7.1.5.1. Definition of Treatment-Emergent

Treatment-emergent AEs are events that meet one of the following criteria:

- Any AEs with onset date of on or after the study drug start date and no later than 30 days after permanent discontinuation of study drug
- Any AEs leading to premature discontinuation of study drug.

7.1.5.2. Incomplete Dates

If the date of onset is incomplete, then the month and year (or year alone if month is not recorded) of onset determine treatment emergent as follows. The event is treatment emergent if the month and year of onset (or year of onset) of the event meets both of the following criteria:

- The same as or after the month and year (or year) of the first dose of study drug
- The same as or before the month and year (or year) of 30th day after the date of the last dose of study drug

If the start date is missing and the stop date is on or before the date of the last dose of study drug plus 30 days, then the event is considered treatment-emergent.

7.1.6. Summaries of Adverse Events and Deaths

A brief summary of AEs will show, by treatment group, the number and percentage of subjects who (1) had any treatment-emergent AE, (2) had any treatment-emergent moderate or severe AE, (3) had any treatment-emergent severe AE, (4) had any treatment-emergent treatment-related AE, (5) had any treatment-emergent treatment-related moderate or severe AE, (6) had any treatment-emergent treatment-related severe AE, (7) had any treatment-emergent SAE, (8) had any treatment-emergent treatment-related SAE, (9) permanently discontinued from study drug due to an AE, (10) had dose reduced or temporarily interrupted due to an AE, and (11) died during study.

The number and percentage of subjects who experienced at least 1 TEAE will be provided and summarized by SOC, HLT and PT. For other AEs described below, summaries will be provided by SOC and PT, and/or by PT as indicated:

- All treatment-emergent AEs by severity
- All treatment-emergent AEs (by PT)
- All treatment-emergent treatment-related AEs (and by PT)
- All treatment-emergent serious AEs (and by PT)
- All treatment-emergent treatment-related SAEs (and by PT)
- All treatment-emergent AEs that caused permanent discontinuation from study drug
- All treatment-emergent AEs that caused temporary interruption of study drug
- All treatment-emergent AEs that caused dose reduction of study drug
- All treatment-emergent AEs that caused permanent discontinuation from study
- All treatment-emergent AEs leading to death

Multiple events will be counted once only per subject in each summary. For data presentation, SOC and HLT will be ordered alphabetically, with PT sorted by decreasing total frequency. For summaries by severity grade, the most severe event will be selected. In addition to the presentation by SOC and HLT, all treatment-emergent AEs will also be presented by preferred term only, ordered by decreasing total frequency.

In addition to the by-treatment summaries, data listings will be provided for the following:

- All AEs (with a flag indicating whether the event is treatment-emergent)
- SAEs (including deaths)
- Subjects who became pregnant during the study
- AEs leading to discontinuation of study or study drug
- Severe AEs
- AEs leading to temporary interruption of study drug
- AEs leading to dose reduction
- AEs leading to death

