7.2.2. Assessment of Severity

The severity grading of AEs will be assessed as described below:

Mild: Awareness of signs or symptoms, but easily tolerated; are of minor irritant type; no loss of time from normal activities; symptoms would not require medication or a medical evaluation; signs and symptoms may be transient, disappearing during continued treatment with study drug; symptoms which do not interfere with subject's daily activities.

Moderate: Discomfort enough to cause interference with usual activities; the study drug may be interrupted. Symptoms which may interfere with subject's daily activities; being within reasonable limits; not excessive or extreme; medium or average extent; study drug may be interrupted.

Severe: Incapacitating with inability to do work or do usual activities; signs and symptoms may be of systemic nature or require medical evaluation; the study drug may be stopped, and treatment for the event may be required. Events which interrupt subject's usual daily activities and may require medical intervention or treatment; study drug may be stopped.

7.3. Investigator Requirements and Instructions for Reporting Adverse Events and Serious Adverse Events to Gilead

Requirements for collection prior to study drug initiation

After informed consent, but prior to initiation of study drug, the following types of events should be reported on the eCRF: all SAEs and AEs related to protocol-mandated procedures.

Adverse Events

Following initiation of study drug, all AEs must be collected, regardless of cause or relationship, until 30 days after last dose of study drug, and be reported on the eCRF as instructed.

All AEs should be followed up until resolution or until the adverse event is stable, if possible. Gilead may request that certain AEs be followed beyond the protocol defined follow up period. AEs ongoing at the time of death are to remain ongoing unless it is confirmed that the event resolved at or prior to the death.

Serious Adverse Events

All SAEs (including deaths), regardless of cause or relationship, that occur after the subject first consents to participate in the study (ie, signing the informed consent) and throughout the duration of the study, including the protocol-required post treatment follow-up period, must be reported on the eCRF and to Gilead Drug Safety and Public Health (DSPH) as instructed. This also includes any SAEs resulting from protocol-associated procedures performed after informed consent is signed.

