
Study Periods/Phases
	
Subjects will be seen in the clinic for a Screening visit (within 14 to 28 days prior to Randomization; within 14 to 60 days for those enrolled under Protocol Amendment 1), a Randomization visit, and during the treatment period at Week 2, 6, 12, 18, and 24 visits. Subjects will be contacted between study visits for assessment of adverse events and concomitant medications. In order to accumulate additional long-term safety data in this population, subjects will continue double-blind treatment (and 12-weekly assessments) until the last subject has been followed up for approximately 24 weeks. As that date approaches, all remaining subjects (including subjects who have already discontinued treatment but are continuing the study) will be contacted to return for the EDBT Period visit. At the end of the double-blind, placebo-controlled treatment period, all subjects who complete the treatment period (including study drug dosing) may continue in the study, at the discretion of the investigator, and receive eleclazine in an OLE. During the OLE period, subjects will continue to undergo periodic required assessments. A safety follow-up visit will occur 30 days after the last dose of study drug. The schedule of follow-up and OLE visits may vary according to country specific requirements.

Schedule of Assessments

The study includes 4 periods: Screening, Double-Blind Placebo-Controlled Treatment (minimum of 24 weeks), Open-Label Extension (OLE), and Follow-up (30 days after last dose). During the Screening phase, baseline CPET as well as implantable cardioverter-defibrillator (ICD) interrogation, where applicable, will be performed and subjects will wear the ZIO[®] XT Patch which will be collected on Day 1. Demographic, medical history, adverse events (AE), concomitant medications, physical examination (PE), ECG, ECHO, and vital signs results will be recorded and samples will be collected for laboratory results.

[figure not shown]
Eligible subjects will be randomized on Day 1. Pharmacokinetic (PK), NT-proBNP and hsTnT samples will be collected, and ECG, ECHO, MLHFQ, and PE including vitals will be performed. Study drug will be dispensed on Day 1 and all subsequent study visits during the double-blind placebo-controlled treatment and the OLE periods.

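### Adverse events are tabulated only as crude percentages although time at risk differs widely between subjects; if one arm stops drug earlier and risk persists, its SAE and special-interest figures can be too low

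*SAP*

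**What the plan says.** **Tables.** SAP 7.1.6 states: "The number and percentage of subjects who experienced at least 1 TEAE will be provided and summarized by SOC, HLT and PT". The serious, related and discontinuation tables follow the same pattern, and "Multiple events will be counted once only per subject in each summary". SAP 7.1.7 summarizes cardiac failure, syncope/dizziness/vertigo and convulsions by preferred term. No rate per person-time, time-to-first-event estimate or fixed-window AE table is planned. SAP 7 plans no formal safety comparison.

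**Time at risk.** Treatment runs to a common calendar end: "subjects will continue double-blind treatment (and 12-weekly assessments) until the last subject has been followed up for approximately 24 weeks" (SAP 1.2). The same section expects 12 months of enrollment and a maximum of about 20 months double-blind. SAP 4.3.1 tabulates exposure up to 84 weeks or more. SAP 2 records that the sponsor ended the study before the double-blind phase was complete.

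**Counting window.** Under SAP 7.1.5.1 an event counts if its onset is on or after the start of drug and "no later than 30 days after permanent discontinuation of study drug". A second criterion, with no date limit, adds "Any AEs leading to premature discontinuation of study drug". Collection of non-serious events has the same limit (Protocol 7.3): "Following initiation of study drug, all AEs must be collected, regardless of cause or relationship, until 30 days after last dose of study drug". SAEs are collected "throughout the duration of the study, including the protocol-required post treatment follow-up period", but the SAE tables in SAP 7.1.6 take only treatment-emergent ones. The overview table counts subjects who "died during study", without the 30-day limit.

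**The concern.** A crude percentage compares arms fairly when subjects in both arms have similar time in which an event can be counted. Here that time depends on entry date and on when the subject stops drug. Randomization balances the first but not the second. An arm with more early stopping contributes fewer weeks, and for an event that keeps occurring over time its percentage falls for that reason alone.

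Safety and tolerability is a secondary objective, and double-blind treatment was prolonged specifically to gather long-term safety data. With no formal comparison planned, readers will set the two percentages side by side. SAEs and the special-interest events matter most.

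**Working it through.** The plan gives no AE or stopping rate, so it has no figure of its own to reproduce on this point. All rates below are assumptions.

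**1. Spread of planned time.** Enrollment of 12 months (52.2 weeks) plus 24 weeks gives 76.2 weeks for the first entrant. The stated maximum of 20 months is 87.0 weeks. Against 24 weeks for the last entrant the ratios are 76.2/24 = 3.2 and 87.0/24 = 3.6. Termination may have left late entrants with less than 24 weeks.

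**2. Mean time at risk.** Assume planned time uniform over 24–76 weeks (mean 50), early stops uniform over weeks 1–24 (mean 12.5), and a 30-day tail (30/7 = 4.3 weeks). With a fraction s stopping early, mean time = (1 − s) × 50 + s × 12.5 + 4.3.
- s = 10%: 45.0 + 1.25 + 4.3 = 50.5 weeks.
- s = 25%: 37.5 + 3.1 + 4.3 = 44.9 weeks, a ratio of 0.89.

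**3. Crude incidence with equal true rates.** For a constant rate λ per week and a window uniform from a to b weeks (tail included), the probability of an event is 1 − [exp(−λa) − exp(−λb)] / [λ(b − a)]. Stopping is taken as unrelated to the event. Completers have windows of 28.3–80.3 weeks and early stoppers 5.3–28.3.

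| True rate, both arms | Completers | Early stoppers | 10% stop | 25% stop | Ratio |
|---|---|---|---|---|---|
| 0.1/year | 9.85% | 3.15% | 9.2% | 8.2% | 0.89 |
| 0.5/year | 39.9% | 14.7% | 37.4% | 33.6% | 0.90 |

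For example, 0.75 × 9.85 + 0.25 × 3.15 = 8.2. With stopping of 15% against 10% the ratios are 0.96–0.97; with 35% against 10% they are 0.82–0.83.

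**4. Masking.** A true 15% excess (0.115 against 0.1/year) with 25% against 10% stopping appears as 9.3% against 9.2%. First events per subject-year at risk recover 11.5 against 10.0 per 100.

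**5. A different stopping model.** With exponential discontinuation and follow-up of 24–76, 24–87 or 4–76 weeks, equal true rates give crude ratios of 0.88–0.93 at 10% against 20% stopping per 24 weeks, and 0.78–0.86 at 10% against 30%. A true rate ratio of 1.5 (20 against 30 per 100 person-years, 10% against 30% stopping, 24–76 weeks) appears as 16.9% against 19.5%, ratio 1.15.

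**6. Where the effect is absent or reversed.**
- Equal stopping: ratio 1.00 in all three follow-up scenarios.
- All risk in the first 4 weeks: ratio 1.00 even at 10% against 30% stopping.
- The extra 15 percentage points of stopping in step 2 each caused by an AE, background 0.5/year: the any-AE percentage is 0.75 × 39.9 + 0.10 × 14.7 + 0.15 × 100 = 46%, against 37%. The arm with more stopping then looks worse.

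**The case against.** **Direction.** A reader might infer that the arm with more early stopping necessarily looks safer than it is. The documents do not support that. Entry dates are balanced in expectation, and neither unequal stopping nor persisting risk is reported. A subject who stops for intolerance has had an AE that SAP 7.1.5.1 counts whatever its date, so AE-driven stopping raises the any-AE figure, as step 6 shows. This objection stands. It confines the point to events unrelated to the reason for stopping.

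**Visibility.** SAP 4.2 gives discontinuation and its reasons by arm, SAP 4.3.1 gives exposure in four-week categories, and SAP 7.1.6 gives AE-driven discontinuation, reduction and interruption. Deaths are counted over the study, and all AEs are listed with a treatment-emergent flag. An imbalance in stopping would therefore be seen. A reader still could not turn it into event-specific rates from the tables, because time to first event is not summarized.

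**Size.** At 90 per arm, 8.2% against 9.2% is about one subject (0.9) and 33.6% against 37.4% about three (3.4). The 95% half-widths of those differences are about 8 and 14 percentage points. The SAP now serves a synoptic report. This is a fair argument for a short supplement instead of a new set of tables.

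**The remedy has its own bias.** A person-time rate assumes a roughly constant hazard, while the regimen has a Day 1 loading dose and a dose change at Week 12. In the earlier multiple-dose study, abnormal dreams began in the first week and had stopped by Day 17 (Protocol 1.2.3). If all risk falls in the first 4 weeks, 25% against 10% stopping gives a correct crude ratio of 1.00 but a spurious rate ratio of about 1.12. This stands, and it is why a rate alone is not enough.

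**Conclusion.** The point holds in conditional form. The planned tables cannot separate a lower event rate from a shorter time at risk, in a design where that time varies more than three-fold and counting closes at a date set by each subject's own stopping.

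The figures exposed are those for treatment-emergent SAEs and the special-interest groups, where the event was not the reason for stopping. If stopping is 25% against 10% and risk is constant, the deficit is about 10%. Across the stopping differences examined it runs from about 4% to about 22%. It is zero with equal stopping or early-onset risk. All these sizes rest on assumed stopping and event rates.

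Two stronger readings are not supported. One is that the spread of entry dates by itself favors an arm. The other is that poor tolerability of eleclazine would be hidden: AEs leading to discontinuation always count, and the overview table counts deaths throughout the study.

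**What to change.** In SAP 7.1.6 (treatment-emergent SAEs) and SAP 7.1.7 (each special-interest group), keep the crude percentages and add by arm:

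- subjects with a first event per 100 subject-years at risk, with time running from first dose to the earlier of the first event and last dose plus 30 days;
- a Kaplan–Meier or cumulative-incidence estimate at Week 24, which does not assume a constant hazard;
- descriptive 95% confidence intervals for both and no test, in keeping with SAP 7.

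State how an AE leading to discontinuation is handled if its onset falls outside that window, so that numerator and denominator match. Add a rule for partial onset dates: SAP 7.1.5.2 classifies them without assigning a day, and SAP 3.6 allows no other imputation.

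**Cost.** A few columns in a small number of tables, built from dose and onset dates already collected, plus the date rule. The rate still assumes a roughly constant hazard, so it should be read beside the Week 24 estimate and the crude percentage and not replace them.
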